5.3.6. Safety Population

The Safety Population will include all participants who received at least 1 dose of study treatment. Treatment groups for this population will be determined according to the actual treatment the participant received regardless of assigned study treatment.

All safety analyses will be conducted using the Safety Population.

5.3.7. Efficacy Population

The Efficacy Population will include all participants with secondary efficacy endpoint data available for both baseline and postbaseline measurements, and this will be used for the analysis of all secondary efficacy endpoints.

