2.2. Study Objectives and Endpoints

[Table 1](#) presents the objectives and endpoints.

Table 1: Objectives and Endpoints

Objectives	Endpoints
Primary	
To determine biologic response in participants with muscle-invasive cisplatin-ineligible or those refusing cisplatin therapy, urothelial carcinoma of the bladder.	For each treatment group, the primary endpoint is the change from baseline in CD8+ lymphocytes within resected tumor.
Secondary	
To evaluate the safety and tolerability of each of the treatment groups.	Safety and tolerability assessed by monitoring the frequency and severity of AEs, including delay in cystectomy due to AEs.
To evaluate the preliminary efficacy of each of the treatment groups.	
• pCR rate, defined as percentage of participants with ypT0N0 in each treatment group.• Major pathological response, defined as residual ypT0/1/a/isN0M0.

Table 1: Objectives and Endpoints (Continued)

Objectives	Endpoints

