7.3. Analysis of the Secondary Efficacy Parameters

7.3.1. Pathological Complete Response Rate

Pathological CR rates at the time of radical cystectomy will be assessed as a secondary endpoint. Pathological CR is defined as ypT0N0 and in situ cancer on the basis of histology evaluation of the TURBT and cystectomy samples by local institutional analysis. The number and percentage of participants with ypT0N0 in each treatment group will be calculated, and 80% CIs will be

estimated using the Clopper-Pearson method. The Efficacy Population will be used for this analysis. All response data will be listed.

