7.3.2. Major Pathological Response Rate

Major pathological response rates at the time of radical cystectomy will be assessed as a secondary endpoint. The number and percentage of participants with ypT0/1a/isN0M0 in each treatment group will be calculated, and 80% CIs will be estimated using the Clopper-Pearson method. The Efficacy Population will be used for this analysis. All response data will be listed.

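### Pathological response rates leave out randomized participants without cystectomy pathology, and Section 7.3.1 of the SAP defines pCR in two ways

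*SAP*

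**What the plan says.** **Denominator.** SAP Section 5.3.7 defines the Efficacy Population as "all participants with secondary efficacy endpoint data available for both baseline and postbaseline measurements" and adds that "this will be used for the analysis of all secondary efficacy endpoints". Section 7.3.1 fixes the timing of the first endpoint: "Pathological CR rates at the time of radical cystectomy will be assessed as a secondary endpoint". Section 7.3.2 does the same for the second: "Major pathological response rates at the time of radical cystectomy will be assessed as a secondary endpoint". Both sections, and Tables 2.2 and 2.3 in Appendix A, use the Efficacy Population, with 80% Clopper-Pearson intervals.

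Section 3 provides follow-up for participants whose cystectomy does not take place, and Section 6.2 counts those who had it. The Full Analysis Set (FAS, Section 5.3.2) holds all randomized participants in their assigned groups, but its listed uses do not include the response rates. Section 10.1 declares that the Efficacy Population definition was updated from the protocol.

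**Definition.** Section 7.3.1 states: "Pathological CR is defined as ypT0N0 and in situ cancer on the basis of histology evaluation". Its next sentence reads: "The number and percentage of participants with ypT0N0 in each treatment group will be calculated". Table 1 in Section 2.2 has "pCR rate, defined as percentage of participants with ypT0N0 in each treatment group" and, for the other endpoint, "Major pathological response, defined as residual ypT0/1/a/isN0M0". The abbreviation list glosses ypT0N0 alone as complete pathological response.

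**The concern.** Both endpoints are post-therapy pathological stages read at surgery. Without surgery there is no postbaseline value, so the planned denominator depends on something that happens after randomization. The SAP foresees missed surgery but does not count those participants in the response analysis.

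These two rates are the SAP's only secondary measures of preliminary efficacy per group. The study is open-label and compares single, double and triple regimens, so the share reaching surgery could differ between groups. Two groups with the same all-randomized response could then report different rates.

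The definition problem is separate and needs no assumption about missing data. A participant whose only residual disease is in situ is a complete responder under one sentence of Section 7.3.1 and not under the next.

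**Working it through.** The SAP states no expected rate, sample size or power for either endpoint, so there is no planned figure to reproduce. It also gives no non-cystectomy rate.

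**Inputs**
- N = 18 (Groups A, B, D, E) and N = 9 (Group C): planned participants, SAP Table 2.
- 80% Clopper-Pearson interval: Sections 7.3.1 and 7.3.2.
- m, the number randomized without pathology, and x, the number of responders: assumed. m = 2 of 18 and m = 1 of 9 borrow the allowance in Table 2 between participants and paired biopsies (18 to 16, 9 to 8).

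**Step 1: size of the shift.** The planned rate is x/(N-m). The all-randomized rate, with missing pathology as non-response, is x/N. Their ratio is N/(N-m):
- N = 18: 18/16 = 1.125, 18/14 = 1.286, 18/12 = 1.500.
- N = 9: 9/8 = 1.125, 9/7 = 1.286, 9/6 = 1.500.

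There is no shift when m = 0 or x = 0.

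**Step 2: rates and 80% intervals**

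| N | x | m | Planned rate | 80% CI |
|---|---|---|---|---|
| 18 | 4 | 0 | 4/18 = 22.2% | 10.1–39.6 |
| 18 | 4 | 2 | 4/16 = 25.0% | 11.4–43.9 |
| 18 | 4 | 4 | 4/14 = 28.6% | 13.1–49.2 |
| 18 | 4 | 6 | 4/12 = 33.3% | 15.4–55.9 |
| 9 | 2 | 0 | 2/9 = 22.2% | 6.1–49.0 |
| 9 | 2 | 1 | 2/8 = 25.0% | 6.9–53.8 |
| 9 | 2 | 2 | 2/7 = 28.6% | 7.9–59.6 |
| 9 | 2 | 3 | 2/6 = 33.3% | 9.3–66.7 |

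The rows with m = 0 are the all-randomized rates. For N = 18 the rises are 2.8, 6.3 and 11.1 points. Every shifted estimate lies inside the all-randomized interval.

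**Step 3: two groups.** Two groups with 4 responders of 18 randomized, one with m = 0 and one with m = 4, would be reported as 22.2% and 28.6%.

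**Step 4: definition.** Each in-situ-only case counted as pCR adds 1/n. At n = 18 that is 5.6 points, for example 4/18 = 22.2% to 5/18 = 27.8% (14.2–45.5). At n = 9 it is 11.1 points, for example 2/9 = 22.2% to 3/9 = 33.3% (12.9–59.9). With a smaller Efficacy Population the step is larger.

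**The case against.** **Replacement enrolment.** Section 3 says further participants will be enrolled until the required paired biopsies are obtained, and Table 2 sets these at 16 (8 in Group C). Each pair needs a surgical sample, so fewer than 16 resected participants is unlikely unless an arm stops early, which Section 3 allows. This stands, and it makes the rows with m = 4 or 6 at N = 18, and m = 2 or 3 at N = 9, less likely. With 16 resected, m = 4 means N = 20 and a factor of 20/16 = 1.25; m = 6 means N = 22 and 22/16 = 1.375. The shift gets smaller but remains.

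**A coherent, declared estimate.** A rate among participants with pathology is prespecified, and Section 10.1 declares the change of population. Counting missing pathology as non-response is itself an assumption, and it understates the rate if any such participant had responded. This stands, and it is a reason to keep the planned version alongside.

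**Little depends on these rates.** No test, threshold or between-group comparison uses them, and Section 3 says the translational endpoints guide the choice of therapies. Table 1.1.1, the disposition table and the response listings let a reader rebuild the all-randomized rate. This limits the seriousness, but neither that rate nor its interval is a planned output.

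**One sentence out of line.** The counting sentence, Table 1 and the abbreviation list agree on ypT0N0. Listing the in situ category under major response does not by itself exclude it from pCR, because that category also contains ypT0. Both points are fair. The contradiction inside Section 7.3.1 remains.

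**Conclusion.** Both parts hold. The pCR definition is contradictory as written, whatever the data turn out to be. The denominator is a weak choice rather than an error: it is prespecified, but it drops participants without surgery from the SAP's only secondary efficacy measures and offers no all-randomized rate beside it.

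If participants without pathology are non-responders, the planned rate is too high by N/(N-m). With the allowance in Table 2 that factor is 1.125, or 2.8 points at 4 responders of 18. Larger shifts need more missed surgery than replacement enrolment makes likely. The value of m and the responder counts are assumptions; the formula is not. The primary CD8+ analysis is unaffected. This should be fixed before the analysis but does not threaten the trial's main result.

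**What to change.** 1. Report both rates in the FAS by assigned group, counting no cystectomy or no evaluable pathology as non-response, with the same 80% Clopper-Pearson intervals. The FAS suits an open-label randomized study because it keeps the assigned groups; the Safety Population (Section 5.3.6) groups by treatment received.
2. Keep the Efficacy Population version as supportive.
3. Amend Section 5.3.7 so that it no longer claims every secondary efficacy endpoint, add the two rates to the FAS uses in Section 5.3.2, and align Sections 7.3.1 and 7.3.2 and Tables 2.2 and 2.3.
4. Reconcile Section 7.3.1 with Table 1 so that one pCR definition applies: ypT0N0, as in Table 1 and the counting sentence, unless the protocol says otherwise.

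**Cost.** Wording in four SAP sections and a second denominator in two tables, from data already collected. The main reported rates fall by the factor (N-m)/N and do not change at m = 0. Participants randomized but never treated, whom Section 4.1.1 foresees, count as non-responders: with 4 responders and one such participant in 18, the rate is 4/18 = 22.2% instead of 4/17 = 23.5% among the treated.

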6. BASELINE, EXPOSURE, AND DISPOSITION

[Appendix A](#) provides a list of data displays. Sample data displays are included in a separate document.

6.1. Demographics, Baseline Characteristics, and Disease History

6.1.1. Demographics and Baseline Characteristics

The following demographics and baseline characteristics will be summarized for the FAS: age, sex, race, ethnicity. Categorical parameters (sex, race, ethnicity) will be summarized by number and percentage. Continuous parameters (age) will be summarized by descriptive statistics (N, mean, standard deviation, median, minimum, and maximum). Age will also be summarized in categories < 65 years and \geq 65 years by number and percentage.

All demographic and baseline characteristic data will be listed.

6.1.2. Baseline Disease Characteristics

The following baseline disease characteristics will be summarized by number and percentage for the FAS: ECOG performance status.

6.1.3. Disease History

The type of urothelial cancer, stage at diagnosis, current stage, disease histology at diagnosis, current disease histology, TNM staging at diagnosis, current TNM staging, time since MIBC diagnosis, cisplatin therapy use, smoking status, history of hydronephrosis, and history of BCG-intravesical installations will be summarized. Categorical parameters will be summarized by number and percentage. Continuous parameters will be summarized by descriptive statistics (N, mean, standard deviation, median, minimum, and maximum) for the FAS.

The TURBT procedure for diagnosis will be summarized using number and percentage for all categorical values including if a radical TURBT procedure was performed and the PD-L1 CPS score category.

Time since diagnosis will be calculated as follows:

$$\text{Time since diagnosis (years)} = (\text{date of randomization} - \text{date of diagnosis} + 1) / 365.25.$$

All disease history data will be listed.

6.1.4. Prior Therapy

The number of prior systemic cancer therapy regimens will be summarized for all participants in the FAS. The component drugs of prior systemic therapy regimens will be coded using the WHO Drug Dictionary. The number and percentage of participants who received each drug will be summarized by WHO drug class and WHO drug PT. The regimen name, component drugs, start and stop dates, route, purpose of the regimen, best response, reason for discontinuation, and date of relapse/progression will be listed.

The number of participants who received prior radiation will be summarized for the FAS. The radiotherapy type, body site, start and stop dates, reason for the regimen, number of fractions received, total dose, and best response will be listed.

The number of participants who had prior surgery or surgical procedure for the malignancies under study will be summarized for the FAS. The date and description of the surgery/procedure will be listed.

6.1.5. Medical History

For participants in the FAS, medical history will be summarized by assigned treatment group. This summation will include the number and percentage of participants with a medical history event for each body system/organ class as documented on the eCRF and coded using MedDRA. All available medical history data will be listed.

6.2. Disposition of Participant

The number and percentage of participants who were randomized, who were treated, who were ongoing with study treatment, who completed study treatment, who discontinued study treatment with a primary reason for discontinuation, who underwent radical cystectomy, who were still in the study, who completed the study, and who withdrew from the study with a primary reason for withdrawal will be summarized for the FAS. The number of participants randomized by country and site will also be provided by treatment group. All disposition information will be listed.

6.3. Protocol Deviations

Protocol deviations and adjudications will be summarized and listed.

6.4. Exposure

For participants in the safety population, exposure to epacadostat, retifanlimab, INCAGN02385, and INCAGN02390 will be summarized descriptively as the following:

- **Number of cycles of epacadostat:** number of cycles with a nonzero dose of epacadostat.
- **Number of cycles of retifanlimab:** number of cycles with a nonzero dose of retifanlimab.
- **Number of cycles of INCAGN02385:** number of cycles with a nonzero dose of INCAGN02385.
- **Number of cycles of INCAGN02390:** number of cycles with a nonzero dose of INCAGN02390.
- **Duration of treatment with epacadostat (days):** date of last dose of epacadostat – date of first dose of epacadostat + 1 – days of interruption.
- **Duration of treatment with retifanlimab (days):** date of last dose of retifanlimab – date of first dose of retifanlimab + 1.
- **Duration of treatment with INCAGN02385 (days):** date of last dose of INCAGN02385 – date of first dose of INCAGN02385 + 1.
- **Duration of treatment with INCAGN02390 (days):** date of last dose of INCAGN02390 – date of first dose of INCAGN02390 + 1.

- **Average daily dose of epacadostat (mg/day):** total actual epacadostat dose taken (mg) / duration of treatment with epacadostat (days).
Total actual dose taken will be calculated based on the information entered in the Drug Accountability Epacadostat eCRF.
- **Average dose of retifanlimab (mg):** total actual retifanlimab dose taken (mg) / number of treatments with retifanlimab.
Total actual dose taken will be calculated based on the information entered in the Dose Retifanlimab eCRF.
- **Average dose of INCAGN02385 (mg):** total actual INCAGN02385 dose taken (mg) / number of treatments with INCAGN02385.
Total actual dose taken will be calculated based on the information entered in the Dose INCAGN02385 eCRF.
- **Average dose of INCAGN02390 (mg):** total actual INCAGN02390 dose taken (mg) / number of treatments with INCAGN02390.
Total actual dose taken will be calculated based on the information entered in the Dose INCAGN02390 eCRF.
- **Epacadostat dose modifications:** number of participants who had epacadostat dose reduction and interruption.
- **Dose delays and dose interruptions:** number of participants with dose delays and dose interruptions.

All exposure data will be listed.

6.5. Study Treatment Compliance

For participants in the safety population, overall compliance (%) for epacadostat will be calculated for all participants as follows:

$$\text{Compliance (\%)} = 100 \times [\text{total dose actually taken}] / [\text{total prescribed dose}].$$

The total prescribed dose is defined as the sum of the doses prescribed by the investigator accounting for dose modifications.

The total actual dose taken will be calculated based on information entered on the Drug Accountability Epacadostat eCRF. If there are dispensed drugs that have not been returned yet, the actual dose taken starting from the dispense date of the unreturned drugs will be imputed by the dose taken as reported on the Dose Epacadostat eCRF.

For participants treated with retifanlimab, INCAGN02385, or INCAGN02390, compliance will be calculated based on infusion records documented by the site staff and monitored by the sponsor/designee.

6.6. Prior and Concomitant Medication

Prior medications and concomitant medications will be coded using the WHO Drug Dictionary. The number and percentage of participants in the FAS for each prior and concomitant medication will be summarized by WHO drug class and WHO drug PT. All medications will be listed.

7. EFFICACY

[Appendix A](#) provides a list of data displays. Sample data displays are included in a separate document.

7.1. Efficacy Hypotheses

The primary hypothesis is that each study treatment assigned in each treatment group given prior to a cystectomy will change the amount of immune cells (CD8+ lymphocytes) within the resected tumor in participants with bladder cancer. Assuming $S_i(t)$ is the log 2 of fold change from baseline function in regard to CD8+ lymphocyte counts, the testing hypothesis is as follows:

- H_0 (null hypothesis): $S_i(t) = 0$
- H_A (alternative hypothesis): $S_i(t) \neq 0$

7.2.2. Subgroup Analyses for Primary Endpoint

Not applicable.

7.2.3. Sensitivity and Supportive Analyses for Primary Endpoint

Not applicable.

7.3. Analysis of the Secondary Efficacy Parameters

7.3.1. Pathological Complete Response Rate

Pathological CR rates at the time of radical cystectomy will be assessed as a secondary endpoint. Pathological CR is defined as ypT0N0 and in situ cancer on the basis of histology evaluation of the TURBT and cystectomy samples by local institutional analysis. The number and percentage of participants with ypT0N0 in each treatment group will be calculated, and 80% CIs will be

estimated using the Clopper-Pearson method. The Efficacy Population will be used for this analysis. All response data will be listed.

7.3.2. Major Pathological Response Rate

Major pathological response rates at the time of radical cystectomy will be assessed as a secondary endpoint. The number and percentage of participants with ypT0/1a/isN0M0 in each treatment group will be calculated, and 80% CIs will be estimated using the Clopper-Pearson method. The Efficacy Population will be used for this analysis. All response data will be listed.

8. SAFETY AND TOLERABILITY

[Appendix A](#) provides a list of data displays. Sample data displays are included in a separate document.

8.1. General Considerations

Summary tables may be replaced with listings when appropriate. For instance, an AE frequency table may be replaced with a listing if it only contains a few unique PTs reported on relatively few participants.

8.2. Adverse Events

8.2.1. Adverse Event Definitions

A TEAE is any AE, either reported for the first time or the worsening of a pre-existing event, occurring after the first dose of study treatment. Analysis of AEs (as discussed below) will be limited to TEAEs, but data listings will include all AEs regardless of their timing in relation to study treatment administration. For purposes of analysis, all AEs will be considered TEAEs unless the AE can unequivocally be defined as not treatment-emergent.

Adverse events will be tabulated by MedDRA SOC and PT. Severity of AEs will be graded using the NCI CTCAE v5. The CTCAE reporting guidelines and grading details are available on the Cancer Therapy Evaluation Program website.

The subset of AEs considered by the investigator to be related to study treatment will be considered to be treatment-related AEs. If the investigator does not specify the relationship of the AE to study treatment, the AE will be considered to be treatment-related. The incidence of TEAEs and treatment-related TEAEs will be tabulated. In addition, serious TEAEs will also be tabulated.

All AE data will be listed.

8.2.2. Adverse Events of Special Interest

Adverse events reported as post-radical cystectomy complications as well as those assessed as immune-related will be coded according to the MedDRA 26.0. Postsurgery complications will be further classified according to the Clavien-Dindo Grading System ([Dindo et al 2004](#)).

8.2.3. Adverse Event Summaries

An overall summary of AEs by treatment group will include the following:

- Number (%) of participants who had any TEAEs
- Number (%) of participants who had any serious TEAEs
- Number (%) of participants who had any Grade 3 or higher TEAEs
- Number (%) of participants who had any TEAEs related to study treatment
- Number (%) of participants who had any immune-related TEAEs
- Number (%) of participants who had any immune-related TEAEs of Grade 3 or higher
- Number (%) of participants who permanently discontinued study treatment because of a TEAE
- Number (%) of participants who temporarily interrupted study treatment because of a TEAE
- Number (%) of participants who had any fatal TEAEs
- Number (%) of participants who had a delay in radical cystectomy due to a TEAE
- Number (%) of participants who had a TEAE leading to hospitalization

The following summaries will be produced by MedDRA term:

- Summary of TEAEs by MedDRA SOC and PT
- Summary of TEAEs by MedDRA PT in decreasing order of frequency
- Summary of TEAEs by MedDRA SOC, PT, and maximum severity
- Summary of Grade 3 or higher TEAEs by MedDRA SOC and PT
- Summary of Grade 3 or higher TEAEs by MedDRA PT in decreasing order of frequency
- Summary of serious TEAEs by MedDRA SOC and PT
- Summary of serious TEAEs by MedDRA PT in decreasing order of frequency
- Summary of treatment-related TEAEs by MedDRA SOC and PT
- Summary of treatment-related TEAEs by MedDRA PT in decreasing order of frequency
- Summary of immune-related TEAEs by MedDRA SOC and PT
- Summary of immune-related TEAEs of Grade 3 or higher by MedDRA SOC and PT
- Summary of treatment-related serious TEAEs by MedDRA SOC and PT
- Summary of treatment-related serious TEAEs by MedDRA PT in decreasing order of frequency

- Summary of nonserious TEAEs by MedDRA SOC and PT
- Summary of TEAEs leading to dose interruption by MedDRA SOC and PT
- Summary of TEAEs leading to discontinuation of study treatment by MedDRA SOC and PT
- Summary of TEAEs with a fatal outcome by MedDRA SOC and PT
- Summary of TEAEs by MedDRA SOC and PT leading to delay in radical cystectomy
- Summary of TEAEs considered as post-radical cystectomy complications by MedDRA SOC and PT

